#### 1. PROTOCOL SYNOPSIS

The present prospective, single-center trial is designed to evaluate the efficacy of CyMedica Orthopedics e-viveTM system, a multifunctional electrotherapy device providing neuromuscular electrical stimulation (NMES), for improving quadriceps strength and accelerating functional recovery in patients managed with total knee arthroplasty (TKA). This post-market clinical trial will involve fellowship-trained Adult Reconstructive orthopaedic surgeons, and include patients who are receiving a unilateral primary TKA. It is hypothesized that the combined preoperative and postoperative use of the CyMedica e-vive NMES can allow for better knee function and allow for a quicker return to function following TKA.

### 1.1 Number Of Sites And Number Of Patients

The study will be conducted at two sites within the Cleveland Clinic Health System (Main Campus, Lutheran Hospital, and Avon Hospital), and involve a total of 66 patients. All study patients will be divided into three groups: (a) NMES therapy both before and after surgery in addition to standard of care physical therapy (PT); (b) NMES therapy only after surgery in addition to standard of care PT; (c) only standard of care PT.

# 1.2 Study Duration

Eligible patients will be evaluated according to the time and events schedule (see Table in section 1.4). Clinical outcomes will be assessed from 4 weeks  $\pm$  5 days before day of surgery and followed up after surgery over a 12 weeks  $\pm$  1 week study period.

#### 1.3 Outcome Assessments

These three groups will be analyzed using several outcome measures including validated patient-reported outcome measures the Knee Injury and Osteoarthritis Outcome Score(KOOS) [1], and Veterans RAND 12 item health survey (VR-12))[2], knee active range of motion (extension, flexion), quadriceps femoris muscle (QFM) strength, the Timed Up and Go Test [3] and the Stair Climb Test. The primary endpoint for the study is QFM strength. However, of secondary interest will be: 1) other physical performance measures (i.e. limb symmetry index and gait speed, activity levels), 2) Visual Analogue Scale (VAS) pain levels [4], on outpatient follow-up and immediately before & after NMES therapy, 3) length of stay, 4) Patient dependence on assistive device, 5) Patient satisfaction measures, 6) Patient discharge disposition, 7) Patient readmission rate. The proprietary app for this product will be used to track device usage (intensity, duration of session, frequency of use), knee range of motion and gait speed.

#### 1.4 Time and Events Schedule

|                              | Preop                                  | Day of Surgery | 3 weeks    | 6 weeks    | 12 weeks  |
|------------------------------|--|----------------|------------|------------|-----------|
|                              | $(4 \text{ weeks} \pm 7 \text{ days})$ | (- 7 days)     | (± 7 days) | (± 7 days) | (± 7days) |
|                              | prior to surgery)                      |                |            |            |           |
| Outcome Scores               | X                                      | X              | X          | X          | X         |
| Range of Motion              | X                                      | X              | X          | X          | X         |
| QFM strength                 | X                                      | X              | X          | X          | X         |
| TUG Test                     | X                                      | X              | X          | X          | X         |
| VAS Pain                     | X                                      | X              | X          | X          | X         |
| Narcotic usage               | X                                      |                | X          | X          | X         |
| Length of Stay               |  | X              |            |            |           |
| Number of outpatient therapy |  |                | X          | X          | X         |
| visits                       |  |                |            |            |           |
| Patient Satisfaction         |  | X              |            |            | X         |
| Readmissions                 |  |                | X          | X          | X         |
| Ambulation assist            | X                                      | X              | X          | X          | X         |

### 2. BACKGROUND

The current standard for rehabilitation after TKA consists of guided exercise therapy for up to 12 weeks after surgery. This includes inpatient, home, and outpatient therapy. The surgery and rehabilitation are highly successful at reducing or eliminating pain experienced preoperatively. However, QFM strength, overall function, and knee range of motion are often worse than preoperative levels for as long as 6 months after surgery and in some cases may persist for many years after that. Such quadriceps strength impairments after TKA have been largely attributed to voluntary activation deficits and can lead to a decrease in functional performance such as decreased gait speed, decreased balance which can lead to falls, and decreased stair climbing & chair rise abilities [5,6]

Since therapy alone does not adequately restore or improve upon the preoperative functional capabilities in a consistent and timely manner, it has been suggested that NMES used adjunctively with postoperative rehabilitation will alleviate the quadriceps muscle activation deficits. Early NMES use after TKA has been shown to: reduce knee extensor lag [7], increase walking speed [8], and improve QFM strength, knee range of motion, and function [5]. However, NMES initiated one month after TKA did not lead to improved QFM strength or function beyond the standard benefits gained from exercise alone [9], thus suggesting that the timing of NMES application after TKA is important.

It has previously been shown that preoperative QFM strength is predictive of postoperative function [10] but the benefit of prehabilitation remains in question [11–13]. To date, there has only been one pilot study assessing the benefits of NMES when initiated preoperatively[14]. This study only included 14 patients (9 NMES, 5 control) but was able to show that preoperative NMES usage may lead to greater QFM strength gains after TKA. Therefore, it will be important to assess the benefits of NMES both preoperatively and postoperatively in order to determine how it will be most beneficial to TKA patients.

### 3. HYPOTHESIS AND SPECIFIC AIMS

**Study Hypothesis:** Our hypothesis is that use of the CyMedica e-viveTM NMES both preop and postop can improve functional outcomes following TKA.

**Specific Aim 1.** Test whether patients treated with preop and postop NMES show improved physical performance measures when compared to postop only NMES group and standard of care group.

**Specific Aim 2.** Test whether patients treated with preop and postop NMES show improved patient-reported outcomes when compared to postop only NMES group and standard of care group.

**Specific Aim 3.** Test whether patients treated with NMES require fewer outpatient physical therapy visits when compared to the standard of care group.

**Specific Aim 4.** Test whether patients treated with NMES have a decreased discharge disposition to extended care facilities as well as shorter length of stay in extended care facilities compared to standard of care group.

**Specific Aim 5**. Test whether patients treated with NMES have decreased 90 day postoperative readmission rates compared to the standard of care group.

**Specific Aim 6.** Test whether patients treated with NMES have decreased dependence of the use of ambulatory assist devices.

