### 4. MATERIALS

### 4.1. Control Group

Control treatment will be standard of care preoperative protocol & standard of care postoperative physical therapy and rehab protocol after TKA. At the end of the study the control group patients will be given the option to cross-over at 12 weeks and receive the NMES device to use.

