#### 5.4. Randomization

The patients will not be informed of their treatment assignment until a minimum of 4 weeks  $\pm$  7 days prior to day of surgery. A computer-based randomization generator (SAS, Inc.) will be used to assign patients into treatment arms in a 1:1:1 ratio, using a block randomization method. Patients in the combined treatment group will be given NMES units for device use beginning at at 4 weeks  $\pm$  7 days before surgery. Patients in the postoperative treatment only group will be given NMES units preoperatively and or upon discharge from the hospital. Those patients who are in the postoperative group only who receive the device preoperatively will be instructed to begin using the device only after their surgery. Patients in the control group will not receive any NMES units but will be given the option to crossover and receive a device at the end of the study.

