# Postoperative Care

Postoperative care will be standardized according to the protocol routinely used at our institution with rapid mobilization, gait training and range of motion [11]. Outpatient physical therapy will be scheduled as needed based on the therapist's assessment of recovery. Physical therapy locations must be Cleveland Clinic affiliated due to the need to use staff who have appropriate training on the NMES device usage to ensure accurate data collection. Pain will be controlled with orally administered long- and short-acting narcotics supplemented by parenteral narcotics as necessary. All study patients will receive standard of care anesthesia protocol.

Following discharge, patients will return for visits with a member of the research team at 3 weeks  $\pm$  7 days, 6 weeks  $\pm$  7 days, 12 weeks  $\pm$  7 days. Data will be collected and reported on the appropriate Case Report Forms at these follow-up visits.

As a last resort, if a patient is unable to keep one of these appointments, he/she will be either be mailed or emailed the OrthoMidas forms so the patient can fill them out. The patient will date and time the forms. They will then send the form back in a pre-addressed envelope. The patients email will be verified by the patient during a clinical visit to ensure accuracy of the correct recipient. Patients not responding to the initial mailer will be contacted by phone and forms may be administered over the phone. The mailers and/or phone calls will allow us to collect all data except the physical function measures. At the completion of the study, patients

will be given a voluntary survey about their experience with the clinical trial, which will be given in person, and or mail and email.

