#### 6.3 Assessments

#### **Data collection**

The study duration will be until 12 weeks  $\pm$  1 week postoperatively. Data will be collected (1) 4 weeks preoperatively, (2) prior to hospital admission for TKA, and (3) at 3, 6, and 12 weeks postoperatively (see table in 1.4). All data will be entered and maintained in REDCap, an electronic data capture tools hosted at Cleveland Clinic [20].REDCap (Research Electronic Data Capture) is a secure, web-based application designed to support data capture for research studies, providing 1) an intuitive interface for validated data entry; 2) audit trails for tracking data manipulation and export procedures; 3) automated export procedures for seamless data downloads to common statistical packages; and 4) procedures for importing data from external sources. Only members of the study team (i.e. the personnel listed on the IRB application) will have access to protected health information of patients included in this study.

The following will be collected on all patients in the study and managed using REDCap:

- 1 MRN
- 2. Name
- 3. Date of birth
- 4. Address
- 5. Phone number
- 6. Email address
- 7. Date of surgery
- 8. Visit dates
- 9. Age at the time of surgery
- 10. Gender: male or female
- 11 BMI
- 12. Comorbidities
- 13. Date of surgery: (month/day/year)
- 14. Any complications (e.g., emergency department visits, infection, reoperation, etc.)
- 15. KOOS, VR-12, and VAS pain questionnaire forms

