#### **Postoperative Assessments**

After surgery, one or more of the following will be collected through the online app and at follow-up visits.

- Device usage patterns (thru app)
- Range of motion of affected knee (thru app and at follow-up)
- TUG test
- Stair Climb test
- QFM strength
- Modified KOOS and VR-12 assessments
- VAS pain score

- Length of stay (hospital, extended care facility)
- 90 day readmission rate
- Discharge Disposition (home vs skilled nursing facility vs inpatient rehabilitation)
- Patient Satisfaction measures
- Any use of an ambulation assist aid
- Activity levels using Misfit Wearables® fitness monitor will be uploaded and incorporated into online app

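### Aim 5 specifies a 90-day readmission rate, but planned follow-up ends at 12 weeks ± 1 week and nothing is scheduled to ascertain readmissions to day 90

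*Combined protocol and SAP*

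**What the plan says.** Section 3, Aim 5, sets out to test whether patients treated with NMES have "decreased 90 day postoperative readmission rates compared to the standard of care group". Section 6.3, Postoperative Assessments, includes "90 day readmission rate" among the items to be collected.

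The follow-up described elsewhere is shorter. The schedule in section 1.4 marks readmissions at 3, 6 and 12 weeks and at no later point, with a window of 7 days either side of the 12-week visit. Section 6.3, Data collection, states "The study duration will be until 12 weeks", with a tolerance of one week, and sections 1.2 and 6.2 give the same end point.

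On the source of the data, section 6.3 says "After surgery, one or more of the following will be collected through the online app and at follow-up visits". Section 7.2 plans a Pearson chi-square test for categorical outcomes, with patients analysed in the group to which they were assigned. Under section 4.1, controls are at the end of the study "given the option to cross-over at 12 weeks and receive the NMES device to use". Section 5.4 also places this option at the end of the study.

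**The concern.** The named endpoint and the planned observation period do not match. A patient who attends the final visit exactly on schedule has been followed for 84 days and cannot supply a complete 90-day readmission status from that visit. The length of observation also differs between patients, because the visit window is two weeks wide. A chi-square test on counts makes no allowance for unequal observation time, and no rule covers patients last seen before day 90.

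What is at stake is the meaning of the reported figure. A rate labelled 90-day would be compared with true 90-day rates from elsewhere, although it was ascertained over roughly 11 to 13 weeks.

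**Working it through.** The plan gives no expected rate, power or sample size for readmission. Its only computed figure (20 per group, section 7.1) is for quadriceps strength and does not bear on this point. The check is therefore of dates.

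**Inputs**
- Horizon: 90 days after surgery (section 3, Aim 5; section 6.3).
- Last visit: 12 weeks ± 7 days (section 1.4).
- Possible second anchor: section 6.2 says "Following discharge, patients will return for visits with a member of the research team at 3 weeks", and section 4.2 puts discharge on postoperative day 1 or 2.
- Planned enrolment: 22 per group, 66 in total (section 7.1).

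**Window of the last visit**
- From surgery: 12 × 7 = 84, and 84 ± 7 gives days 77 to 91, which is 15 permitted days. Days 90 and 91 reach the horizon: 2 of 15. The other 13 of 15 (86.7%) fall short.
- From discharge on day 1: days 78 to 92, with 3 of 15 reaching day 90.
- From discharge on day 2: days 79 to 93, with 4 of 15 reaching day 90.

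**Days unobserved, counting from surgery**
- On-time visit: 90 − 84 = 6 days (6/90 = 6.7%).
- Earliest permitted visit: 90 − 77 = 13 days (13/90 = 14.4%).
- Visit dates spread evenly over the window: (13 + 12 + … + 1 + 0 + 0)/15 = 91/15 = 6.1 days on average, so about 93% of the 90 days is covered.

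**Share of patients last seen before day 90.** The documents give no distribution of visit dates, so these are assumptions:

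| Assumed visit dates | Share before day 90 |
|---|---|
| Uniform, days 77 to 91 | 87% |
| Triangular around day 84 | 95% |
| Truncated normal, mean day 84, SD 2 to 5 days | 92% to 99.7% |
| Truncated normal, mean day 88, SD 2 to 5 days | 79% to 81% |
| Uniform, counted from discharge on day 1 / day 2 | 80% / 73% |

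Most patients fall short in every case tried.

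**Events outside the observed period.** The documents give no readmission rate or timing. Assume, for scale only, a 90-day risk of 5% to 10% spread evenly over the period. Expected events missed per group = 22 × risk × (days unobserved/90).
- All visits on day 84: 22 × 0.05 × 6/90 = 0.07, to 22 × 0.10 × 6/90 = 0.15.
- All visits on day 77: 22 × 0.05 × 13/90 = 0.16, to 22 × 0.10 × 13/90 = 0.32.

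On these assumptions the expected loss is well below one event per group.

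**The case against.** The strongest reply is that the team may intend to take readmissions from the chart. The 90-day rate is itself a listed item. The same list holds hospital length of stay and discharge disposition, which ordinarily come from the hospital record. Section 6.3 collects the medical record number, the surgery date and complications such as emergency visits and reoperation, and section 5.3 already uses the electronic record to find patients. This stands to the extent that a day-90 reading is feasible, so one cannot say that late readmissions will be missed. But the plan states neither a source nor a cut-off date for it. Where section 6.3 does mean a record source, it names one: operative data come from the operative and anaesthesia records. The mail and telephone fallback in section 6.2 serves missed scheduled visits, not contact after week 12.

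It is also fair to say that the effect is small. The window is the same in all arms, so a difference between arms would arise only if visit timing differed by arm. Readmission is one of several secondary interests in section 1.3.

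Two stronger inferences are tempting and are not supported:

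- A reader might infer that control crossover contaminates the readmission comparison. If readmissions are collected only up to the 12-week visit, observation stops at the point where a control may receive the device. Crossover becomes relevant only if ascertainment is extended to day 90, and then for 6 days after an on-time visit and at most 13. The intent-to-treat rule in section 7.2 already keeps such patients in their randomised arm.
- A reader might take 1/22 = 4.5 percentage points, the change in the control rate from one readmission, as the size of the error. That is the weight of any single event. It does not show that an event would be lost.

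**Conclusion.** The contradiction is real: a 90-day endpoint is paired with follow-up that, as written, usually ends before day 90. Followed literally, the plan yields a rate over a variable period of 77 to 91 days from surgery, or up to day 93 if visits are counted from discharge. The nominal shortfall is 6 days and the largest is 13.

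That most patients would be seen before day 90 is an inference, since no visit dates are given. It would fail only if about half or more attended at the very end of the window. The likely consequence is slight under-counting, similar across arms, on a secondary outcome. It does not touch the primary endpoint, and the documents do not support a claim of between-arm bias. The change is worth making because the reported quantity would otherwise not be the one named, and the correction is cheap.

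**What to change.** State in section 6.3 and in the schedule (section 1.4) that readmissions for every randomised patient are ascertained from the health-system record on or after day 90 from surgery, whatever the date of the 12-week visit. The cost is one chart check per patient after the last visit, in a record system the trial already uses, plus a line of text in each place. A brief call to pick up admissions to outside hospitals is optional. It would add up to 66 calls, mostly after the stated end of study.

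If ascertainment is extended to day 90, record the date on which any control receives the device and report how many had it before day 90. No change to the analysis population is needed.

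Alternatively, redefine the endpoint as readmission through the 12-week visit, or to a fixed day 84, and report the observation time. A fixed day 84 would still need a record check for anyone seen on days 77 to 83. Either definition should be carried through Aim 5 and the assessment list so that the sections agree, and the plan should say whether visit weeks are counted from surgery or from discharge.

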### 4. MATERIALS

### 4.1. Control Group

Control treatment will be standard of care preoperative protocol & standard of care postoperative physical therapy and rehab protocol after TKA. At the end of the study the control group patients will be given the option to cross-over at 12 weeks and receive the NMES device to use.

# 4.2. Combined Treatment Group

This treatment group will be given the CyMedica Orthopedics e-vive system 4 weeks  $\pm$  7 days before day of scheduled surgery. The patients will begin using the unit until the day before surgery.

Patients will resume using the unit immediately following discharge (POD1 or POD2) + 7 days to take account of a bulky standard of care postoperative dressing, and continuing throughout the first 12 weeks postoperatively. During both preoperative and postoperative phases, patients will be instructed to use the device three times per day while doing activities, 20 minutes each session for 12 weeks.

# Usage and Compliance

The use time will be recorded by the device, which is capable of transmitting the information securely to an online application. The usage will be recorded from before surgery, and at the 3, 6, and 12 week visits in order to determine patient compliance with using the device. The acceptable minimum usage to be considered "compliant" with the protocol (for statistical analysis) are as follows:

#### Time Period

|                                   | 4 weeks prior to
Day of surgery | Discharge from hospital to 3 week visit | 3 week visit to
6 week visit | 6 week visit to
12 week visit |
|-----------------------------------|------------------------------------|---|---------------------------------|----------------------------------|
| Usage
Recommendation           | 3X per day, 20 min sessions        | 3X per day, 20 min sessions             | 3X per day, 20
min sessions  | 3X per day, 20
min sessions   |
| Minimum Usage
Compliance (80%) | 3X per day, 16 min sessions        | 3X per day, 16 min sessions             | 3X per day, 16
min sessions  | 3X per day, 16
min sessions   |

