# 4.3 Postoperative only Treatment Group

This treatment group will be given the CyMedica Orthopedics e-vive system only upon discharge after surgery and will be asked to use the device as described in section 4.2.

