therapeutic intensity level that each patient can tolerate. Due to the differences in body habitus as well as anatomic variances of motor nerve branch distributions which may both alter muscle response to electric current, this will be done for each individual patient that will be using the NMES device. Previous studies have determined that the level needed for the NMES device to deliver a therapeutic dose is based on an intensity that will elicit a quadriceps muscle contraction with either visual or palpable superior patellar glide[15–17]. During the patient's preoperative visit at the 4 week mark, each patient will be evaluated using the NMES device by designated trained research personnel who will determine the level of device intensity that is needed to cause superior patella glide, while ensuring the patient is able tolerate the intensity level. The intensity level will then be recorded and monitored through the device application. Patients will be instructed that they need to use the NMES device at least at the level that was determined to be therapeutic, but may increase the intensity as much as they can tolerate. To achieve maximum effective delivery of therapeutic NMES doses in static positions, we will have the patient place their leg that is going to be operated on in a recommended position between 60 to 75 degrees of knee flexion as much as possible while using the device. This will ensure the muscle will be stimulated near its optimal length-tension relationship to maximize the level of evoked force and muscle tension as well as minimizing patient discomfort and muscle fatigue associated with NMES use[15,18,19].

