### 8. PATIENT INCENTIVE PLAN

In an effort to help bring patients back for all visits and increase device use compliance, patients will be offered \$25 for the 3, 6, and 12 week postoperative visits. In addition, those patients who maintained 80% compliance will be offered a \$200 gift card at the end of the study. The maximum amount a patient may receive is \$275. In addition, parking will be provided for each postoperative visit (\$10/per visit). All patients will be given an activity monitoring device made by Misfit Wearables® at the beginning of the study.

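### The first postoperative compliance window runs from discharge although section 4.2 permits use to resume up to 7 days later, and the 80% rule does not say how use is aggregated

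*Combined protocol and SAP*

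**What the plan says.** All references are to the combined protocol and SAP.

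- **Start of postoperative use (section 4.2).** "Patients will resume using the unit immediately following discharge (POD1 or POD2) + 7 days to take account of a bulky standard of care postoperative dressing". Section 4.3 carries this over to the postoperative-only group, whose patients "will be asked to use the device as described in section 4.2". Both device arms are therefore covered: 2 x 22 = 44 of the 66 planned patients.
- **Compliance table (section 4.2, Usage and Compliance).** There is one preoperative period and three postoperative periods. The first postoperative period is "Discharge from hospital to 3 week visit". In every period the recommendation is "3X per day, 20 min sessions" and the minimum, labelled 80%, is "3X per day, 16 min sessions". The text above the table says that the label is meant for statistical analysis.
- **3-week visit (section 6.2, Postoperative Care).** Day 21, plus or minus 7 days.
- **Use of the label.** Section 8 says that "those patients who maintained 80% compliance will be offered a" $200 gift card. Section 7.2 specifies analysis by assigned group (intent-to-treat) and describes no analysis of compliant patients.

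Nothing in the document says whether use is checked each day or summed over a period, or how the periods combine into one label.

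**The concern.** The start rule and the scoring rule in section 4.2 do not fit together. One allows up to 7 days without use; the other counts those days as days on which use was due. A patient can follow the first exactly and fail the second.

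The 80% row has a separate ambiguity. It shortens the session from 20 to 16 minutes and leaves the frequency at three per day. Taken literally as a daily check, it requires every session on every day. Taken as a total, it tolerates missed sessions. Two analysts could label the same patient differently.

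At stake are the compliance rates that the trial reports, any analysis that splits patients by the label, and a payment that makes up $200 of the $275 maximum.

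**Working it through.** **Inputs.** Recommended 3 x 20 min and minimum 3 x 16 min per day (table in section 4.2). Discharge on postoperative day 1 or 2, and a permitted delay of up to 7 days (section 4.2). 3-week visit on day 14 to 28 (section 6.2). Surgery is day 0.

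**The plan's own figure.** Per session 16/20 = 80%. Per day (3 x 16)/(3 x 20) = 48/60 = 80%. The stated 80% is reproduced on both counts.

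**First postoperative period, latest permitted start, no session missed.** Let W = visit day minus discharge day. The share of recommended minutes is (W - 7)/W, and the minimum is 48 x W minutes.

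| Visit day | Discharge day | W | Days of use | Minutes done | Minimum | Share |
|---|---|---|---|---|---|---|
| 14 | 1 | 13 | 6 | 360 | 624 | 46% |
| 14 | 2 | 12 | 5 | 300 | 576 | 42% |
| 21 | 1 | 20 | 13 | 780 | 960 | 65% |
| 21 | 2 | 19 | 12 | 720 | 912 | 63% |
| 28 | 1 | 27 | 20 | 1,200 | 1,296 | 74% |
| 28 | 2 | 26 | 19 | 1,140 | 1,248 | 73% |

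The share reaches 80% only if (W - 7)/W is at least 0.8, that is W of at least 35 days. The longest permitted W is 27. The patient therefore fails on summed minutes, and on a daily check as well, because the delay days have no use at all.

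**Longest delay that still allows 80%.** 0.2 x W: 3.8 to 4.0 days for a day-21 visit, and 2.4 to 5.4 days across the visit range. All are shorter than the 7 days permitted.

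**If all postoperative periods were pooled to the 12-week visit (day 77 to 91).** W is 75 to 90, and (W - 7)/W runs from 68/75 = 91% to 83/90 = 92%. The same patient passes.

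**If the delay days are left out of the denominator.** For a day-21 visit, 12 of 12 or 13 of 13 days: 100%.

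**Daily check against total.** One missed session per week leaves 20/21 = 95% of recommended minutes. This fails a literal three-per-day check and passes a summed rule. In a 21-day period (63 sessions), 12 missed sessions leave 51/63 = 81% and 13 leave 50/63 = 79%, so a summed rule tolerates up to 12.

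**The case against.** The strongest reply is that the effect depends on how the label is built. No text says that one failed period makes a patient non-compliant, and pooling rescues the late starter. This stands as a limit on the claim. It does not remove the conflict, because the table sets out separate periods and pooling is nowhere stated.

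The second reply is that 48 of 60 minutes is 80% of daily use, so the table may already intend total minutes. That is fair. A reader might infer that the rule as written fails anyone who misses a session. The document supports only the narrower point that the aggregation rule is missing.

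Third, the late start is a worst case. The document does not say how many patients would start more than about 4 days after discharge, so the number mislabelled cannot be estimated.

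Three further inferences are tempting and are not supported:

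- **Bias in the primary comparison of quadriceps strength.** Section 7.2 analyses patients as assigned, and no planned test uses the label.
- **A link between the label and prognosis through slow wound recovery.** Section 4.2 attributes the delay to a routine dressing, not to slow healing.
- **Intensity as a missing part of the rule.** Section 6.2 asks patients to "use the NMES device at least at the level that was determined to be therapeutic", and intensity is recorded through the app. The compliance rule is a measure of use time, so leaving intensity out is a design choice and not a contradiction.

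**Conclusion.** The point holds in a limited form. The permitted start and the first postoperative scoring window in section 4.2 conflict. A patient in either device arm who starts on the last permitted day and then follows the recommendation fully cannot reach 80% in that window at any permitted visit date; the best attainable share is 74%. The missing aggregation rule is a second, smaller gap.

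This rests on three assumptions: the 7 days are an allowance after discharge, the window is scored on its own from discharge, and the patient does not exceed 60 minutes a day. To make up the shortfall by day 21, use would have to average 960/13 = 74 or 912/12 = 76 minutes a day, above the recommendation.

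The consequence is confined to reported compliance, any later analysis by compliance, and the gift card. It should be corrected before any patient is labelled, but it does not threaten the intent-to-treat result.

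**What to change.** Reconcile the start rule and the table in section 4.2 with section 8, leaving every treatment instruction as it is:

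1. Define compliance in each period as logged minutes divided by recommended minutes (60 per day), with the existing 80% threshold (48 minutes per day on average).
2. In the first postoperative period, leave out of the denominator the days between discharge and first use, up to the 7 that section 4.2 permits. Days beyond 7 count as missed. This needs no clearance date; section 4.2 has no clearance step.
3. State how the periods combine into one label, for example whether each must be met or minutes are pooled.
4. Use the same definition for the gift card in section 8.
5. If an analysis by compliance is intended, describe it in section 7.2. If not, say that the label is descriptive.

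The cost is a rewording and one date of first postoperative use per device patient. That date belongs in the study records, because the app is given a dummy surgery date (section 6.3) and cannot place the windows by itself. There are two trade-offs. A summed rule accepts some missed sessions, and a patient who delays for a reason other than the dressing receives the same allowance.
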